Preliminary data: Informational alerts and peer comparison nudges have proven effective in other studies to change behavior. The PROMPT HF trial done in a university medical center demonstrated that informational alerts were associated with an increase in the number of GDMT medication classes prescribed (primary endpoint) from 19% to 26% ($p=.03$). One study compared individual audit feedback, peer comparison, and the combination, in a four-group design to influence clinician opioid prescribing in emergency care sites. They found a significant decrease in pills per prescription in the peer comparison arms.

We lack adequate knowledge about how to improve HF prescribing with nudges. Despite promising initial studies on the value of information alerts to improve HF prescribing, the improvements in prescribing were seen exclusively with beta-blockers, not in prescribing of SGLT2 inhibitors and MRAs – where the largest gaps exist in VA.

We need more information on whether combining nudges into multicomponent interventions is more effective.

A systematic review reported that only five of 48 nudge (10%) interventions in the literature were multicomponent; none of the studies were performed in the VA. For example, an evaluation active choice patient dashboard (delivered by email) with and without peer comparison to increase statin prescribing amongst PCPs found that only the active choice plus the peer comparison arm was associated with increased statin prescribing but not the active choice or the usual care arm alone. However, in these multicomponent trials, it is not clear which component is most impactful. Comparative effectiveness nudge trials are needed due to relative advantages and potential tradeoffs of each intervention. Further, research is needed to how nudges interact with one another and whether they may crowd each other out. In this proposal, we will evaluate whether informational alerts, peer comparison, or the combination of the two, is most effective.

This research will generate comparative evidence on which types and combinations of behavioral nudges work best. This study targets an HF treatment gap (SGLT2 and MRA) in which no prior nudge studies have demonstrated efficacy.

Our target population is clinicians in primary care and cardiology who are the main clinicians who treat HF. To incorporate the voice of the Veteran, we will meet with Veteran and Family Advisory Panel at SAVAHCS for feedback on the study design.

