2.0 AIMS

Aim 1. Conduct a process evaluation ['PROCESS EVAL'] to develop two nudge strategies, an informational alert and peer comparison feedback, to encourage clinicians to prescribe MRA and SGLT2 inhibitors.

Aim 2. Evaluate preliminary outcomes ['NUDGE EFFECTIVENESS'] of the two nudge strategies to improve HF prescribing using the RE-AIM framework.

- a) Evaluate the preliminary Effectiveness of the alert and peer comparison strategies in a four-group design.
 - i) The four-groups to be compared are: control (no intervention), peer comparison email alone, information alert alone, and peer comparison/informational alert in combination. We will examine provider prescribing behavior and patient outcomes.
- b) Evaluate the implementation outcomes of the two nudge strategies.
 - i) We will report the following PRISM/RE-AIM outcomes: intervention, recipients, external environment, infrastructure, Reach, Adoption, and Implementation.

We hypothesize that an informational nudge and peer comparison will each increase prescribing compared to usual care (no nudge intervention). Further, we hypothesize that the combination of the two strategies will be more effective than either strategy alone.

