4.0 STUDY DESCRIPTION

4.1 STUDY DESIGN

TIMELINE				
	Startup Activities	Pre Nudge (control period)	Active Nudge Period	Post intervention period
Month (-12) to Month 0	Month 0-6	Month 7-9	Month 10-12	Month 13-18
	PROCESS EVALUATION			
	Interviews with clinicians; focus group with Veteran Council	Follow-up interviews and questionnaires with clinicians, follow-up focus group with Veteran Council		Focus groups with clinicians.
	NUDGE EFFECTIVENESS			
Patient data collection (to create peer comparison emails, need prior 12 month prescription information)				

AIM 1. – PROCESS EVALUATION. At the beginning of the study, we will conduct **interviews and focus groups** of SAVAHCs primary care and cardiology clinicians to understand clinician workflow, barriers, and feedback on proposed nudge interventions. We will also obtain **conduct focus groups with SAVAHCs Veteran Advisory Council**. After completing Aim 2, near the end of the study we will interview clinicians again and have them complete questionnaires regarding their opinions on the nudge interventions.

AIM 2. NUDGE EFFECTIVENESS. This is a pragmatic trial of cardiology and primary care clinicians at a single VA medical center. The trial will include a 3-month preintervention (observation) period and 3-month intervention period. In the intervention period, clinicians will be randomized to one of four nudge arms: usual care, informational alert, peer comparison feedback, and combination of alert and peer comparison.

Table 2. Study design			
	Peer comparison		
		Yes	No
Informational alert	Yes		
	No		

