Data Analysis. Though randomization occurs at the clinician level, we will measure outcomes at the patient level. The dataset used for analysis will be limited to all MRA- and SGLT2i-eligible identified in the HF dashboard (this includes patients in the control group-- even though no alert will be generated). This sample allows us to compare differences in rate of prescription of the same patient types between the three intervention groups and control group. Descriptive statistics will comprise patient and provider demographics, including practitioner specialty and type, and part-time status. General Linear Models (GLM) and chi square tests will be used to compare continuous and categorical demographic variables, respectively, between the three interventions and control groups. Significant differences will be defined with p values < 0.05. Generalized Linear Mixed Models (GLMM) will be used to compare rates of both SGLT2 or MRA (in separate, univariate analyses) between the nudge intervention and control groups. Practitioner specialty and type, part time status, years of experience, and patient visit number will be included as covariates, and the patient, clinician, and clinic assignment (clustering of providers), will be entered as random effects. While these covariates are strata for randomization, it is unlikely, due to the study sample size, that all combinations will be equally distributed between the two groups. We will therefore need to employ statistical control of these potential influences. The GLMMs will be specified as random coefficient models or growth curve models to evaluate changes in prescription behavior over time, as well as between groups. Models will include the preintervention baseline as a covariate and will use all patient visits until the conclusion of the data collection period. Significant differences will be concluded with odds ratio and 95% confidence intervals that do not contain the value 1.0. This statistical approach

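### No analysis is specified for the second hypothesis, that the combined nudges beat either nudge alone: every named treatment comparison is against control

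*Combined protocol and SAP*

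**What the plan says.** Section 2.0 (Aims) sets two hypotheses. The first is that each nudge raises prescribing relative to usual care. The second reads "we hypothesize that the combination of the two strategies will be more effective than either strategy alone". Section 1.0 (Background, preliminary data) states the comparative purpose, "we will evaluate whether informational alerts, peer comparison, or the combination of the two, is most effective", and notes that "research is needed to how nudges interact with one another and whether they may crowd each other out".

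Section 4.1 randomizes clinicians to "usual care, informational alert, peer comparison feedback, and combination of alert and peer comparison". Table 2 lays these arms out as alert yes/no by peer comparison yes/no.

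Section 8.0 (Data Analysis) describes the sample as allowing a comparison of prescription rates "between the three intervention groups and control group". The main generalized linear mixed model (GLMM) is to "compare rates of both SGLT2 or MRA (in separate, univariate analyses) between the nudge intervention and control groups". The secondary safety model is likewise intervention against control. The power paragraph plans a 5-point gain per intervention arm over usual care, with 168 patients per group and 672 in total.

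**The concern.** A stated hypothesis should lead to a named estimate. The second hypothesis compares the combination arm with each single-nudge arm, and section 8.0 contains no such comparison. Its GLMM sentence can mean all nudges pooled against control, or each arm against control. Neither reading answers the hypothesis.

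Three decisions are therefore left until after the data are seen: which contrasts to draw, whether the combination must beat both single nudges or only one, and how to handle the error rate. A reader given only arm-versus-control results may also compare verdicts, noting that the combination is significant against control and a single nudge is not. That does not test the difference between them.

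**Working it through.** **Hypotheses against analyses**

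| Statement in the plan | Comparison needed | Named in section 8.0? |
|---|---|---|
| Hypothesis 1 (2.0): each nudge v usual care | alert v control; peer v control | Yes, if arms are not pooled |
| Hypothesis 2 (2.0): combination v either alone | combination v alert; combination v peer | No |
| Which strategy is most effective (1.0) | contrasts among the nudge arms | No |
| Crowding out (1.0, a research need only) | alert x peer interaction | No |

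**Inputs.** Section 8.0 gives a 5-point difference, 80% power, alpha 0.05 (two-sided assumed), 168 per arm and about 60 clinicians. It gives no control rate of new SGLT2 or MRA prescriptions, so p0 is assumed and varied. No effect is given for combination v single. I assume each nudge adds 5 points and the effects add, so the combination is 5 points above either nudge alone.

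**The plan's own figure.** n per arm = [1.96·√(2p̄(1−p̄)) + 0.84·√(p0(1−p0) + p1(1−p1))]² / (p1−p0)², where p̄ is the mean of p0 and p1.

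At p0 = 0.25% and p1 = 5.25%: (0.4533 + 0.1924)² / 0.0025 = 167. So 168 is approached two-sided only at a near-zero control rate. At control rates of 1%, 5%, 10% and 19% the formula gives 211, 435, 686 and 1,059. The point does not depend on this figure, but it fixes the most favourable case.

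**Power of combination v one single nudge, 168 per arm.** Power = Φ[(0.05 − 1.96·SE0)/SE1], with SE0 pooled and SE1 unpooled.

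- p0 = 5%, so 10% v 15%: SE0 = 0.0361, SE1 = 0.0360. (0.05 − 0.0707)/0.0360 = −0.58, power 28%. 95% CI half-width 1.96 × 0.0360 = 7.1 points.
- p0 = 0.25%, so 5.25% v 10.25%: SE0 = 0.0292, SE1 = 0.0290. (0.05 − 0.0572)/0.0290 = −0.25, power 40%. Half-width 5.7 points.

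| Assumed control rate | Power, combination v one nudge | Power, beating both | n per arm for 80% (one contrast) |
|---|---|---|---|
| 0.25% | 40% | 27% | 448 |
| 1% | 38% | 25% | 488 |
| 5% | 28% | 16% | 686 |
| 10% | 23% | 11% | 906 |
| 19% | 18% | 8% | 1,222 |

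**Interaction.** Suppose the combination does no better than a single nudge, an interaction of −5 points. A Wald test of p11 − p10 − p01 + p00 at 168 per arm then has 38% power at a 0.25% control rate and 21% at 5%.

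**Clustering.** Randomization is by clinician, with 672/60 = 11.2 patients each. An assumed intraclass correlation of 0.05 gives a design effect of 1 + 10.2 × 0.05 = 1.51 and an effective 168/1.51 = 111 per arm. The 28% and 40% fall to about 20% and 29%.

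**The planned effect read literally.** If every intervention arm, including the combination, gains the same 5 points over usual care, the planned difference for hypothesis 2 is zero.

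**The case against.** The strongest reply is that section 8.0 also speaks generally of differences between groups and of the significance of treatment group. A four-level group term in the planned GLMM would yield combination-versus-single odds ratios without refitting. This stands in part. A reader might infer that the plan cannot test hypothesis 2, or rules the test out, and the text does not support that. What is missing is the specification: permitting a contrast does not name it, its success rule or its error control.

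A reader might also infer that the 2x2 layout calls for factorial main effects as the primary analysis, with arm-versus-control comparisons wasting half the data. The documents do not support this. Hypothesis 1 is stated against usual care with no nudge, which the arm-versus-control contrasts answer directly, and the plan calls the design four-group. Nor is the gain assured. At an assumed 5% control rate, arm v control (5% v 10%, 168 per arm) has 41% power. A main effect on 336 v 336 has 58% if effects add (7.5% v 12.5%), but only 21% if every nudge arm reaches 10% (7.5% v 10%). With the 1.51 design effect these become 29%, 42% and 15%.

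Crowding out is raised as a research need and is neither an aim nor a hypothesis, so its absence from section 8.0 is a lesser matter. Finally, Aim 2 describes its outcomes as preliminary. That can justify an exploratory label, but it does not justify leaving a stated hypothesis without an analysis.

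**Conclusion.** The point holds as a gap in specification. Every treatment comparison named in section 8.0, and the sample size, is against control, so hypothesis 2 has no specified analysis. That conclusion rests on the text alone.

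The size of the problem rests on assumptions: the control rate, additive 5-point effects, equal arms of 168, a two-sided 0.05 level and no clustering. Under these, one combination-versus-single contrast has about 28% power at a 5% control rate and about 40% near 0.25%, the most favourable case compatible with the planned 168. Clustering by clinician lowers both. Interval half-widths of about 6 to 7 points exceed the 5-point effect itself. The trial can therefore estimate these differences but is unlikely to settle them, and a non-significant result would not show that the combination adds nothing.

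**What to change.** In section 8.0:

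1. Keep the three arm-versus-control contrasts, unpooled, as the analysis of hypothesis 1.
2. Fit the GLMM with a four-level group term, or equivalently with alert, peer comparison and their interaction.
3. Pre-specify combination v alert alone and combination v peer comparison alone as the analysis of hypothesis 2, each with an odds ratio and 95% CI. State whether both must favour the combination, and how multiplicity is handled.
4. Report the alert x peer interaction with its CI as an exploratory estimate of crowding out, and name the scale. For cells of 5%, 10%, 10% and 15%, which add exactly in percentage points, the interaction odds ratio is (0.1765 × 0.0526)/(0.1111²) = 0.75. An odds ratio below 1 therefore need not mean crowding out in percentage points.
5. State that the contrasts in items 3 and 4 have low power and will be read from estimates and intervals. State also that hypothesis 2 will not be inferred from one arm being significant against control and another not.

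The cost is a paragraph of text and a few contrasts from a model already planned, with no new data or patients. The small downside is more reported intervals, most of them wide.

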5.3 INCLUSION/EXCLUSION CRITERIA

Activity	Aim 1.
Interview, focus groups of clinicians	All clinicians in Primary Care and Cardiology
Veterans and Family Advisory Council focus group	All participants at Council meeting
	Aim 2.
Patient record review to deliver nudges (CPRS alerts and peer comparison emails) to clinicians	
Patients meeting these criteria:
 
Inclusion Criteria:
 
 • HF patient • Scheduled cardiology or primary care appointment • Not being prescribed SGLT2 or MRA class medication 
Exclusion Criteria:
 
 • eGFR < 20 ml/min/1.73m² or potassium > 5.0

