8.0 DATA ANALYSIS & STATISTICAL CONSIDERATIONS

Power calculation. One study reported a 14% absolute increase in beta-blocker prescription with enhanced alert compared to usual alert/usual care. Another reported a 7% absolute increase in new prescription of any GDMT in 30 days, also driven by beta-blocker. We anticipate a 5% absolute increase in new prescriptions (SGLT2 or MRA) per intervention arm, compared to usual care. We are anticipating a lower treatment effect because SGLT2 inhibitors are newer, potentially seen as requiring interdisciplinary collaboration, and MRAs require serial lab monitoring. To detect this difference with an 80% power and alpha of 0.05, a sample size of 168 patients who are eligible to activate the alert are required in each treatment group, for a total study sample size of 672 patients encounters. We anticipate that we can achieve this number of patient encounters across the approximately sixty participating clinicians including any possible attrition.

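### The trial is sized on one outcome, most naturally a composite of new SGLT2 or MRA prescription, but the analysis models only each drug separately, names no primary test, and leaves about six comparisons unadjusted.

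*Combined protocol and SAP*

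**What the plan says.** All references are to the combined protocol and SAP.

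- **Section 8.0, Power calculation.** The planning assumption is "We anticipate a 5% absolute increase in new prescriptions (SGLT2 or MRA) per intervention arm, compared to usual care". With power set at 80% and alpha at 0.05, the stated requirement is "a sample size of 168 patients who are eligible to activate the alert are required in each treatment group". Over four groups the plan puts this at 672 encounters. No control-arm rate, sidedness or division of alpha is given. One of the two precedents cited for the effect is a composite: "Another reported a 7% absolute increase in new prescription of any GDMT in 30 days, also driven by beta-blocker".
- **Section 8.0, Data Analysis.** The models "compare rates of both SGLT2 or MRA (in separate, univariate analyses) between the nudge intervention and control groups". The same paragraph describes one dataset and three intervention groups set against control. The decision rule is "Significant differences will be concluded with odds ratio and 95% confidence intervals that do not contain the value 1.0", and it is repeated later in the section.
- **Section 5.4.2.** The number of new prescriptions of either class is listed as a data item. No model is attached to it.
- **Section 2.0.** Each nudge is hypothesised to beat usual care, and the combination to beat either nudge alone.

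No section names a primary outcome, a lead drug, a lead contrast, a testing order or a multiplicity adjustment.

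**The concern.** On the natural reading of the power paragraph, the outcome that justifies the sample size has no model, while its two components each have one. Because no test is designated as primary, a favourable interval for any one drug in any one arm meets the plan's rule for significance. The trial could then be reported as positive on a result for which it was not sized, at an error rate well above the 5% in the power statement. This matters because sections 1.0 and 1.1 say the study will show which nudge, or combination of nudges, works best.

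**Working it through.** **1. The plan's own figure.** 4 × 168 = 672, so the total agrees with the group size. The 168 cannot be checked directly, because no control rate is stated. The usual pooled formula for two proportions is

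n = [z₁₋α/₂ √(2p̄(1−p̄)) + z₀.₈ √(p₀(1−p₀) + p₁(1−p₁))]² / 0.05², with p₁ = p₀ + 0.05.

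It returns 168 only for a control rate of about 0.2% to 0.35% (two-sided) or about 1% (one-sided). That is a separate problem. What matters here is that the calculation covers one outcome and one comparison at alpha 0.05.

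**2. Number of tests.** Outcomes modelled: 2 (section 8.0). Arms against control: 3 (section 8.0). 2 × 3 = 6. The count is derived, not stated.

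**3. Chance of at least one false positive, each test at 0.05 two-sided.**

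- If independent: 1 − 0.95⁶ = 26.5% for six tests; 1 − 0.95³ = 14.3% for three.
- With the control arm shared: simulate four arm estimates for each of two drugs, with correlation ρ between drugs. Form z = (arm − control)/√2 and reject when |z| > 1.96 (400,000 draws, no true effects).

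| ρ between drugs | six tests | three tests, one outcome |
|---|---|---|
| 0 | 23.5% | 12.6% |
| 0.3 | 23.0% | 12.6% |
| 0.5 | 22.0% | 12.6% |
| 0.7 | 20.2% | 12.5% |
| 0.9 | 17.3% | 12.6% |

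The documents do not give ρ, so the whole range is shown. Modelling two drugs rather than one outcome adds between 17.3 − 12.6 = 4.7 and 23.5 − 12.6 = 10.9 percentage points. The rest comes from three uncorrected arms.

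**4. Price of correcting across three arms.** Holm's first step uses 0.05/3. For a 5-point rise, two-sided, with assumed control rates and no allowance for clustering by clinician:

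| assumed control rate | n per arm, 0.05 | n per arm, 0.05/3 | power at 168, 0.05 | power at 168, 0.05/3 |
|---|---|---|---|---|
| 1% | 211 | 282 | 70.5% | 54.0% |
| 5% | 435 | 580 | 41.2% | 25.6% |
| 10% | 686 | 915 | 28.2% | 15.6% |

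The required size rises by about a third (282/211 = 1.34; 915/686 = 1.33). Holm's later steps are less strict, so 0.05/3 is the worst case.

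**The case against.** **The word *or* may mean each drug.** The Data Analysis paragraph uses it that way, and the power paragraph justifies its effect size drug by drug. A reader might therefore go too far in saying that the powered outcome is never analysed; the documents do not settle this. The single effect, the single sample size and the any-GDMT precedent favour the composite. On the other reading there are two powered outcomes at an undivided 0.05, so the multiplicity problem stands.

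**The contrasts are not fixed.** One phrase in section 8.0 could mean all nudges pooled against control, and another speaks of two groups. With one pooled contrast per drug there would be two tests, and 1 − 0.95² = 9.75% if independent. But the same paragraph sets three intervention groups against control, and section 2.0 makes separate claims for each nudge. In the other direction, adding the combination-versus-single hypotheses gives ten tests and about 25% to 33%. Section 8.0 writes no such contrast, so that figure is not the plan's error rate.

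**The aim is preliminary.** Section 2.0 says so, and strict error control in a single-centre preliminary study is a matter of judgement. That would carry weight if the plan only estimated effects. It claims 80% power and declares significance.

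**A tempting further claim is dilution**, meaning that patients already on one drug weaken that drug's model. It requires entry by lacking either drug. Section 5.3 says "Not being prescribed SGLT2 or MRA class medication", which may equally mean on neither, in which case there is no dilution. Even on the either-drug reading, the planned odds ratios barely move. Take the 22% and 39% use in section 1.0 and assume independence: 0.39 × 0.78/(1 − 0.22 × 0.39) = 33% would already take an MRA. With an assumed 5% versus 10% among those at risk, the odds ratio is 2.11 at risk and 2.07 overall. The unclustered z is 1.42 (112 per arm) and 1.40 (168 per arm).

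**Conclusion.** The point holds on two counts. First, the plan provides no analysis of the outcome on which the trial is most naturally read as sized. Second, whichever way that outcome is read, the plan has no designated primary test and an unadjusted rule for significance. Followed as written, with three arms each compared with control for two drugs, the family-wise error is about 17% to 23% for between-drug correlation from 0.9 down to 0. The figures assume equal arms, a shared control and no true effects. They do not depend on the unstated control rate or on which patients enter each drug's denominator. The documents do not support going further and saying that drug-specific effects are materially diluted.

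**What to change.** In the Data Analysis paragraph of section 8.0:

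1. Name one primary outcome: new prescription of at least one of SGLT2 or MRA that the patient was not taking at the index visit. Define the index visit.
2. Name three primary contrasts, each intervention arm against control, tested with Holm: smallest p-value against 0.05/3, next against 0.05/2, last against 0.05. Replace the rule that any interval excluding 1.0 is significant.
3. Report the SGLT2 and MRA models, each in patients not on that drug at index, and the combination-versus-single contrasts as secondary estimates with intervals and no significance claims.
4. Use the same outcome definition in the Power calculation paragraph, and restate the power of 168 per group under the adjusted threshold and a stated control rate.

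The data are already to be collected (section 5.4.2), and neither randomisation nor nudge delivery changes. There are two costs. The 80% power rested on an undivided alpha and no longer holds: either power falls or the required number rises by about a third. The drug-specific results also become secondary. If the sponsor meant each drug as a powered outcome, the power paragraph must say so and the adjustment must cover all six comparisons.

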
Your patient has been identified in VA HF Dashboard as potentially eligible for an SGLT2 inhibitor. This alert is provided for informational purposes.
 
SGLT2 inhibitors are indicated in the 2022 ACC/AHA HF Guidelines (URL link provided) for patients with HFrEF (EF≤40%, NYHA class II-IV HF). Contraindications include urinary tract infection, eGFR < 25, type I diabetes.
 
Relevant data for this patient include: Prescription for beta blocker No prescription for ACE inhibitor LVEF 40% BNP 1550 Renal function: eGFR > 25
 
Suggested actions: Prescribe empagliflozin 10mg daily Alert primary care
 
If prescribing: Recommend checking renal function after starting therapy; reduce diuretic; watch for dehydration
	
Dear Dr. _____,
 
SAVAHCS Cardiology is working on new ways to help clinicians improve their patient's HF treatment. Based on AHA/ACC guidelines and the VA HF Dashboard, you have patients who could be on an SGLT2 inhibitor but have not been prescribed one.
 
Among eligible patients, your rolling 90-day SGLT2 prescribing rate: XX% [one of the following] Average of your peers at SAVAHCS: XX% Your top performing peers at SAVAHCS: XX%
 
If you have any questions, please email study coordinator XXX
 
Sincerely, XXXX Clinical Research Coordinator XXXX Study Principal Investigator

Focus group with SAVAHCS Veteran and Family Advisory Council

[figure not shown]
We will meet twice virtually with the Advisory Council during the study. We will ask for their feedback on their perceptions of study benefit and any suggestions for improvement. Unlike the other focus groups and interviews with clinicians, we will only take notes, but no audio

recording will occur. We will not ask for any individually identifiable information, only general feedback on the study.

Aim 2. NUDGE EFFECTIVENESS

Table 2. Study design			
	Peer comparison		
		Yes	No
Informational alert	Yes		
	No		

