5.4.2 SUBJECT EVALUATIONS

Aim 1.

Subject	Data	Data source
Clinician	Verbal feedback: nudge intervention, workflow Quantitative measures of intervention suitability: questionnaires (Acceptability, Appropriateness, Feasibility) & Clinician general demographics: sex, practice site, specialty/subspecialty, and percent full-time effort, years of experience	Interview, focus group (see attached Interview Guides) Questionnaires (administered via VA Redcap)
Veteran and Family Advisory Panel	Feedback on intervention, workflow	Focus Group

Aim 2.

Subject	Data	Data source
Patient (12 months before baseline, during and post-nudge)	Name, full SSN, dates, demographics, vitals, zip-code level median household income, clinical encounters, Charlson Comorbidity Index, and medications; # alerts delivered, # new HF prescriptions (MRA or SGLT2), # HF	CPRS, HF Dashboard, CDW/VINCI

	medication discontinuations, adverse events, mortality	
--	--	--

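### The prescribing models adjust for clinician traits, visit number and an undefined pre-intervention baseline but for no patient characteristic, so chance case-mix differences between arms go uncorrected, at a modest cost in efficiency

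*Combined protocol and SAP*

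**What the plan says.** All of this is in the combined protocol and SAP.

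- **Unit of analysis (8.0).** "Though randomization occurs at the clinician level, we will measure outcomes at the patient level".
- **Fixed covariates (8.0).** "Practitioner specialty and type, part time status, years of experience, and patient visit number will be included as covariates". Later in the same section: "Models will include the preintervention baseline as a covariate". Section 8.0 does not say what that baseline is. Section 4.3 describes measuring SGLT2 and MRA prescribing rates over the three months before the nudges, which is presumably what is meant.
- **Random effects (8.0).** The covariate sentence continues: "and the patient, clinician, and clinic assignment (clustering of providers), will be entered as random effects".
- **Patient data collected (5.4.2, Aim 2).** "demographics, vitals, zip-code level median household income, clinical encounters, Charlson Comorbidity Index, and medications".
- **Laboratory values (5.3).** Patients are excluded on eGFR and potassium, so both must be read to settle eligibility.
- **Use made of the demographics (8.0).** GLMs and chi-square tests "will be used to compare continuous and categorical demographic variables, respectively, between the three interventions and control groups", with significance at p < 0.05. Nothing in section 8.0 carries these variables into the outcome model.

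**The concern.** The outcome is a decision about one patient, and it plausibly depends on that patient's age, comorbidity, renal function, potassium and existing heart-failure drugs. None of these is in the model. Because clinicians are randomized, patients arrive in whole panels, about 15 per arm, and a few unusual panels can shift an arm's case mix.

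Section 8.0 itself argues that its listed covariates, although randomization strata, will probably not balance at this sample size and so need statistical control. Patient factors are not strata at all, so the argument applies to them with more force.

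Restricting the dataset to eligible patients does not settle the matter. Section 5.3 admits any heart-failure patient with a scheduled appointment who is not on the drug, subject to the two laboratory limits, and sets no LVEF limit. Case mix within the analysis set can therefore vary widely. At stake are some power and the credibility of each contrast if the arms turn out to differ in an obvious patient characteristic.

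**Working it through.** **Inputs.** From section 8.0: 168 patients per arm, about 60 clinicians, a 5-point absolute increase, 80% power, alpha 0.05. Assumed: equal allocation, so 60/4 = 15 clinicians per arm and 168/15 = 11.2 patients per clinician; two-sided testing; and the control rate, the clinician-level ICC of the patient covariates and their prognostic strength, none of which the documents give.

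**1. The plan's own figure.** The 168 per arm cannot be reproduced, because no control new-prescription rate is stated. With n = [1.96·√(2p̄(1−p̄)) + 0.842·√(p0(1−p0)+p1(1−p1))]²/0.05², the requirement is 167 at a control rate of 0.25%, 435 at 5%, 686 at 10% and 1161 at 22%. At 168 per arm, before clustering, power is 0.41, 0.28 and 0.19 for the last three.

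**2. Chance imbalance in one patient covariate (in SD units).** SD of the arm difference in means = √[(2/168)(1 + 10.2·ICC)]:

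- ICC 0: 0.109
- ICC 0.05: 0.134
- ICC 0.10: 0.155
- ICC 0.20: 0.190

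Multiplying by ln(OR per SD) and by 1.96 gives the 95% range of the shift in an arm-versus-control odds ratio:

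- ICC 0.05, OR 1.5 per SD: 0.134 × 0.405 × 1.96 = 0.107, so 0.90 to 1.11
- ICC 0.20, OR 2 per SD: 0.190 × 0.693 × 1.96 = 0.258, so 0.77 to 1.29
- ICC 0, for comparison: 0.92 to 1.09 (OR 1.5) and 0.86 to 1.16 (OR 2)

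For scale, 10% versus 15% is an OR of (0.15/0.85)/(0.10/0.90) = 1.59 (log 0.463), and 22% versus 27% is 1.31 (log 0.271). The weakest shift is 0.107/0.463 = 23% or 0.107/0.271 = 39% of the planned effect on the log scale. The strongest is 0.258/0.463 = 56% or 0.258/0.271 = 95%. These are chance shifts in either direction, not bias. Adjustment for specialty and the pre-intervention baseline, ignored here, would reduce them.

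**3. What adjustment gains.** Simulation of one nudge arm against control: 15 clinicians per arm, 11 patients each, clinician intercept SD 0.3 on the logit scale, one patient prognostic score, 800 runs, logistic model with cluster-robust errors and t on 28 df.

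| Control vs nudge | OR per SD | Case-mix ICC | Power, unadjusted | Power, adjusted |
|---|---|---|---|---|
| 10% vs 15% | 1.5 | 0 | 0.235 | 0.234 |
| 10% vs 15% | 1.5 | 0.10 | 0.231 | 0.251 |
| 10% vs 15% | 3 | 0 | 0.251 | 0.275 |
| 10% vs 15% | 3 | 0.10 | 0.216 | 0.270 |
| 22% vs 27% | 2 | 0 | 0.177 | 0.169 |
| 22% vs 27% | 2 | 0.10 | 0.133 | 0.161 |
| 10% vs 25% | 1.5 | 0 | 0.916 | 0.919 |
| 10% vs 25% | 3 | 0.10 | 0.890 | 0.936 |

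Over all 18 settings run, the change lay between −0.8 and +5.4 points. Monte Carlo error is about 1 to 2 points per figure, so small differences cannot be told from none.

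**4. Precision.** At 10% versus 15%, OR 3 per SD and ICC 0.10, the SD of the log odds ratio went from 0.376 to 0.389 on adjustment, while the median estimate moved from 0.48 to 0.55. The ratio of estimate to SD rose from 0.48/0.376 = 1.28 to 0.55/0.389 = 1.41. Power improves because the estimate moves away from zero, not because the interval shrinks.

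**The case against.** The strongest reply is that the plan already does a good deal. It prespecifies clinician covariates, a baseline and three levels of random effects, and limits the data to eligible patients. Specialty and the baseline will absorb part of any stable difference between panels, and the laboratory exclusions narrow two candidate covariates. The simulation contains none of those plan features, so it does not show what patient covariates would add on top of them. Part of the imbalance in step 2 is ordinary sampling variation, present even at ICC 0 and already reflected in the confidence interval. All of this stands, and it holds the expected gain to modest size. It does not close the gap: if the baseline is a clinician-level rate, it cannot describe differences among patients within a panel, and a random effect does not correct an imbalance that has occurred.

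A long covariate list would also be unwise. At an assumed 10% in control and 15% in each nudge arm, there are 168 × 0.10 + 504 × 0.15 = about 92 events for the combined outcome, and fewer in each single-drug model. LVEF is not in the section 5.4.2 list. It appears in the prototype alert in section 4.3 ("LVEF 40% BNP 1550 Renal function: eGFR > 25"), which usual-care and email-only clinicians do not receive. Both points stand and shape the fix.

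A reader might infer that the arm comparisons are biased or invalid. The documents do not support that: clinicians are randomized and clinician-level variation is modelled. Nor do they support saying that the models ignore baseline altogether, since a pre-intervention baseline is included.

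**Conclusion.** The omission is certain on the text: no patient characteristic is named in either prescribing model, although several are collected. On this count the analysis is valid but somewhat less efficient, and more exposed to chance differences in case mix, than it need be.

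The gain from adjustment is better control of that imbalance and roughly 0 to 5 points of power. The size rests on assumed control rates of 10% to 22%, 1.5 to 3 times the odds per SD, and case-mix ICC of 0 to 0.10. The gain is close to nil when the patient factors are weak or do not cluster by clinician.

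Two larger claims might be drawn and should not be. Adjustment would not narrow the odds-ratio interval (step 4). Nor would it rescue the sample size: at control rates of 5% or more, power at 168 per arm is at most 0.41 even before clustering. The point is worth acting on because the change is cheap, not because the analysis fails without it.

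**What to change.** In section 8.0, name a short set of patient covariates for both GLMMs, each taken as the last value before the nudge period and available in all four arms. For example: age, Charlson index, eGFR and number of other heart-failure drug classes already prescribed, with potassium added in the MRA model. Use this model for every arm contrast.

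- Add LVEF only if it is confirmed to be available for usual-care and email-only patients.
- State how a missing laboratory value will be handled.
- Define the pre-intervention baseline, including whether it is a clinician-level rate.
- Keep the between-arm demographic comparison descriptive, and state that it will not be used to choose covariates. The plan does not say that it would be, but a fixed list removes the doubt.

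The cost is a few sentences in section 8.0 and about four or five model degrees of freedom, which matters a little if events are few. The suggested variables come from data collected under section 5.4.2 or read for eligibility under section 5.3, so no new data collection should be needed.
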